### Secondary Objective Analysis

We will analyze the change in pulmonary arterial pressure by serial echo within 72 hours of initiation of iNO. We will also compare the pulse oximeter to inspired oxygen ratio.

Current Version	9/10/2020	IRBNet #: 1170748
Date:		
Previous Version		Page 16 of 25
Date:		

## Potential Risks and Benefits

### Potential Benefits

If our primary hypothesis is correct, the infant enrolled in the iNO arm may have the benefit of being a survivor without BPD. The infant in the placebo arm will have the same risk of surviving with BPD as in current standard of care.

### Potential Risks:

A potential risk associated with iNO is methemoglobinemia. This risk is minimal as we are using low concentrations of iNO. Occasionally an extremely preterm infant is unstable and performing echocardiogram could cause oxygen desaturation and a temporary increase in FiO2 requirement. Heart failure has been described as a potential risk for iNO treatment. However, this complication is noted only among the patients with ischemic heart disease or myocardial dysfunction. No severe side effects of iNO have been reported at the starting dose of 20 ppm. We will not include any infants with myocardial dysfunction noted on the initial echocardiogram. We will start weaning iNO treatment if worsening of hemodynamic status is noted on serial echocardiograms based upon the recommendations of our cardiologists. Very rarely, nitric oxide can chemically react with oxygen to make nitrogen dioxide (NO2) that can cause inflammation of the airways if the level exceeds beyond 5 parts per million.

### Mitigation of Risks:

We will measure levels of methemoglobin with blood gases as is current standard of care in the NICU. The first methemoglobin level will be checked within 4-8 hours of treatment initiation, and then repeated every 24-48 hours during the intervention. Methemoglobinemia can be reversed by stopping the iNO.

Our device has an alarm set at 0.7ppm for live monitoring of NO2 that is set well below the threshold for any adverse effect.

Study team will seek clearance from the clinical team before performing echocardiogram to ensure the safety of the infant. If an infant is clinically unstable, study echocardiogram can be delayed or cancelled

During the course of study, the attending clinicians may request unmasking of intervention (iNO or placebo) only if oxygenation index is higher than 40 for at least 4 hours or if there is risk of

---

Current Version 9/10/2020 IRBNet #: 1170748  
Date:

Previous Version Page 17 of 25  
Date:

death due to hypoxic respiratory failure without starting iNO. If the infant is on iNO, treatment will continue. If the infant is on placebo, iNO treatment may be allowed. The PI will be notified immediately. A protocol violation will be filed and intention to treat principle will apply.

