### **Secondary Objective/Aim/Goal/Hypothesis:**

Secondary objective is to show that iNO treatment of extremely preterm infants with early PH will decrease the pulmonary artery pressure and improve the oxygenation within 72 hours of intervention. The change in pulmonary artery pressure and oxygenation from

Current Version Date:	9/10/2020	IRBNet #: 1170748
Previous Version Date:		Page 5 of 25

initiation of treatment () to 3 days later (approximately 72 hours later) will be compared for the two treatment arms.

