## Study Procedures

## Subject Recruitment and Screening

The study will commence after IRB approval and OSP clearance and full execution of agreements with Thrasher Foundation and Mallinckrodt. The research team members indicated on the

---

[figure not shown]
Current Version	9/10/2020	IRBNet #: 1170748
Date:		

Previous Version  
Date:

Page 9 of 25

delegation log will screen the NICU census daily for infants who may be eligible for the study. If an infant is identified as potentially eligible through review of the medical records, permission will be sought from the attending neonatologist to approach the parents about study participation. After informed parental consent by a research team member, all eligible infants (per step 1 inclusion criteria above) will be screened by echocardiography at 48-96 hours of life to identify infants with early PH. If an echocardiogram is ordered by the clinical team at this time point, a study echo will not be performed and the data will be retrieved from the clinically indicated echo. If an infant is critically ill and unable to tolerate the procedure as determined by attending clinicians, echocardiogram can be delayed up to 96 hours of age. Any significant clinical finding, e.g. pericardial effusion, large PDA, ventricular dysfunction or any major structural anomaly will be disclosed to the clinical care team. All infants will be managed by the clinical teams in NICU. Eligible infants (per step 2 inclusion /exclusion criteria cited above) will be enrolled in the randomized controlled trial for treatment with iNO or placebo as shown in Figure 1. Infants who have no evidence of pulmonary hypertension on the screening echocardiogram will have no further research intervention activity, but their data will be collected (comparison(reference) group).

Figure 1: Study Enrollment Plan

Diagnosis of PH will be based on peak velocity of tricuspid regurgitation ( $TR_{max}$ ), PDA gradient or end systolic interventricular septal position. We will calculate right ventricular (RV) pressure gradient by modified Bernoulli equation (RV pressure = 4 x ( $TR_{max}$ )). Pulmonary artery pressure

Current Version 9/10/2020  
Date:

IRBNet #: 1170748

Previous Version  
Date:

Page 10 of 25

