## Study Visits:

[figure not shown]
Infants with early pulmonary hypertension will be randomized to the treatment group or the placebo group (see randomization plan). iNO or placebo treatment will start at 20 ppm. Treatment will continue for 2 weeks or until resolution of pulmonary hypertension, whichever comes first.

Current Version	9/10/2020	IRBNet #: 1170748
Date:		
Previous Version		Page 12 of 25
Date:		

To ensure the safety and evaluate the clinical response to iNO treatment, we will perform serial echocardiograms as shown in figure 2.

Figure 2

Time Line for Serial Echocardiography

\*PMA: Post Menstrual Age  
+ PH: Pulmonary Hypertension

Since the data of SpO2 & FiO2 are available in all infants, their ratios (SF ratio) will be calculated as markers of improved oxygenation. SF ratio has the advantage of avoiding invasive arterial blood sampling in situation when umbilical arterial line is unavailable. It is a reliable noninvasive surrogate for PaO2: FiO2 ratio to identify children with severe lung disease. Respiratory Severity Score (RSS= FiO2 X Mean airway pressure (MAP)) will be monitored for infants on mechanical ventilation since the data of mean airway pressure will be available. Significant response to iNO treatment will be defined as 20% improvement in SF ratio or resolution of pulmonary hypertension (assessed by echo) within 72 hours. Serial echocardiograms will be performed every 24-48 ± 12 hours until 14 days of life irrespective of the length of treatment.

Current Version 9/10/2020  
Date:

IRBNet #: 1170748

Previous Version  
Date:

Page 13 of 25

If PH is resolved during the 2-week treatment window or after the completion of the 2-week treatment protocol, we will start weaning the iNO dose by decreasing to 15 ppm. Weaning will continue to 10, 5, 4, 3, 2 and 1 ppm every 4 hours. During the weaning process if SF ratio decreased by 20%, iNO /Placebo dose will be increased to the minimum dose where  $\text{FiO}_2$  and  $\text{PaO}_2$  were stable. Weaning can be resumed after 12 hours following the above guidelines. The iNO weaning process described above is the current standard of care in our NICU for infants with PH. If pulmonary hypertension recurs in the first 2 weeks of life after stopping the treatment, iNO/Placebo treatment will be resumed based upon the randomization at the time of enrollment.

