## Study Outcome Measures (Endpoints)

- Maternal demographics (listed under the data collection section of the protocol)
- Infant measures (listed under the data collection section of the protocol)

Current Version Date:	9/10/2020	IRBNet #: 1170748
Previous Version Date:		Page 14 of 25

- Incidence of death or BPD measured at 36 weeks post menstrual age (yes or no)
  - BPD will be defined as need for supplemental oxygen for at least 28 days. Severity of BPD will be determined at 36 weeks postmenstrual age. Infants with no need for supplemental oxygen will be classified as mild BPD. Continued requirement for supplemental oxygen (<0.3 FiO2) will be considered moderate BPD. Infants requiring >0.3 FiO2 and or positive pressure respiratory support will be diagnosed with severe BPD. The need for continuing oxygen therapy will be determined by a room air challenge. We will prospectively collect data that will allow us to define BPD as recommended by the 2018 NICHD report
- Pulmonary arterial pressure based on serial echocardiograms)
- Oxygen saturation level (average for each 24-hour period after enrollment)
- Arterial pressure and oxygen saturation will be measured up to 2-weeks or until the treatment is discontinued, whichever is shorter.

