## Data Collection and Follow-up for Withdrawn Subjects

Subjects who are withdrawn from the study will not be included in the final analysis. All AEs and SAEs will continue to be collected on withdrawn subjects throughout hospitalization, and that data will be reviewed by the DSMB when necessary.

---

Current Version 9/10/2020 IRBNet #: 1170748  
Date:

Previous Version Page 18 of 25  
Date:

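### The secondary comparison of pulmonary artery pressure has no rule for echocardiograms cancelled for instability or for death before 72 hours

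*Combined protocol and SAP*

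**What the plan says.** The secondary objective is that iNO will "decrease the pulmonary artery pressure and improve the oxygenation within 72 hours of intervention", with the change from treatment start to about 72 hours compared between arms. The Secondary Objective Analysis gives the PAP analysis in one sentence: "We will analyze the change in pulmonary arterial pressure by serial echo within 72 hours of initiation of iNO." A second sentence adds the ratio of pulse oximeter saturation to inspired oxygen. The Primary Objective Analysis names a t test or a non-parametric equivalent for continuous variables and says the short-term benefits will be compared similarly.

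PAP has no source other than echo. Subject Recruitment and Screening says: "Diagnosis of PH will be based on peak velocity of tricuspid regurgitation", with the ductal gradient as second choice and septal position as third.

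The safety rule under Mitigation of Risks is: "If an infant is clinically unstable, study echocardiogram can be delayed or cancelled." Study Visits schedules repeat scans: "Serial echocardiograms will be performed every 24-48 ± 12 hours until 14 days of life irrespective of the length of treatment." The same section lists assessments at 24 ± 6, 48 ± 6 and 72 ± 12 hours.

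No section gives a missing-data method, an analysis set for PAP, or a rule for death before the 72-hour echo. Intention to treat is invoked only for unmasking. On withdrawals the plan says: "Subjects who are withdrawn from the study will not be included in the final analysis."

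**The concern.** Cancelling a scan in an unstable infant is a sensible safety rule and is not in question. Its statistical consequence is that whether a PAP value exists can depend on the infant's condition after randomisation. Death before 72 hours removes the later value altogether. If iNO changes stability in either direction, the infants with values are no longer the groups that randomisation made comparable. A t test on the available changes then estimates an effect in infants stable enough to be scanned, not in all those randomised.

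At stake is a stated secondary objective, with 34 infants per arm. The response definition in Study Visits also uses resolution of pulmonary hypertension on echo within 72 hours, so the gap reaches that as well.

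**Working it through.** The documents give no PAP standard deviation, expected change, missing rate or early death rate, so there is no stated figure to reproduce. The 34 per arm was set for the primary outcome and enters here only as a count. Everything numerical in steps 2 to 4 is assumption.

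**1. How much the repeat echoes protect.** At 24-hour spacing an infant has scans near 24, 48 and 72 hours, and losing one leaves two. At 48-hour spacing, which the every-24-to-48-hours wording also allows, the scans fall near 48 and 96 hours. Only the first normally lies within 84 hours (72 + 12), so one cancellation can remove every post-baseline value.

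**2. Illustration in mmHg, both directions.** Assume PAP changes by -12 (iNO) and -8 (placebo) in infants with an echo, and by +2 in either arm in living infants whose echo was cancelled. With fractions mP (placebo) and mI (iNO) missing:

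Full difference = [-12(1 - mI) + 2mI] - [-8(1 - mP) + 2mP] = -4 + 14mI - 10mP.

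The comparison of available changes always gives -4.0.

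| Missing: placebo, iNO | Full difference | The value -4.0 is |
|---|---|---|
| 10%, 3% | -4.58 | 13% too small |
| 15%, 5% | -4.80 | 17% too small |
| 20%, 8% | -4.88 | 18% too small |
| 15%, 15% | -3.40 | 18% too large |
| 3%, 10% | -2.90 | 38% too large |
| 5%, 15% | -2.40 | 67% too large |
| 8%, 20% | -2.00 | 100% too large |

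The first three rows mean about 3 vs 1, 5 vs 2 and 7 vs 3 infants out of 34. Deaths cannot be put in this table, because PAP after death is undefined.

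**3. Bias in SD units.** Let the least stable fraction m of an arm have no value, with correlation r between instability and PAP change. The observed arm mean shifts by -r·φ(z)/(1 - m), where z is the normal quantile at 1 - m. At r = 1 the shift is 0.1086 for m = 5%, 0.1950 for 10%, 0.2743 for 15% and 0.3500 for 20%. With iNO at 5% missing, the bias against iNO is:

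- placebo 10%: 0.1950 - 0.1086 = 0.086 SD at r = 1, and 0.043 at r = 0.5
- placebo 15%: 0.2743 - 0.1086 = 0.166 SD, and 0.083
- placebo 20%: 0.3500 - 0.1086 = 0.241 SD, and 0.121

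Swapping the arms reverses the sign. Equal loss gives no bias in this model, only lost precision. Step 2 differs on that point because it assumes that infants without an echo gain nothing from iNO.

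**4. Effect on the test.** With all 34 per arm observed, the difference detectable with 80% power at two-sided 0.05 is (1.960 + 0.842) × √(2/34) = 0.68 SD. With 27 per arm it is 0.76 SD. A t-test simulation (6,000 runs per scenario) gave:

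| Missing: placebo, iNO; r | Type I error, no effect | Power, true benefit 0.68 SD | Mean estimate, SD |
|---|---|---|---|
| none | 5.0% | 78% | 0.68 |
| 15%, 5%; 0.5 | 6.0% | 66% | 0.59 |
| 20%, 5%; 0.5 | 7.3% | 59% | 0.56 |
| 20%, 5%; 1 | 20% | 49% | 0.44 |

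**The case against.** The strongest reply is that little may be lost. The rule allows delay as well as cancellation. Scans are repeated, and the analysis sentence refers to serial echo within 72 hours rather than one fixed scan. A missed scan therefore need not remove an infant. This stands as far as it goes, but the plan does not say how earlier or late scans are used, and under the wider spacing there may be only one. Death still removes the 72-hour value.

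The trial is masked, so cancellations should not follow knowledge of the arm. That also stands, but it does not prevent imbalance that arises because treatment affects stability.

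The scope is narrow. Death is an event in the primary composite. For oxygenation the plan says the saturation and inspired-oxygen data "are available in all infants, their ratios (SF ratio) will be calculated as markers of improved oxygenation", so that part needs no echo, although early deaths affect it too.

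A repeated-measures model is not a complete answer. It assumes that missingness is explained by observed data, and it extrapolates PAP beyond death. Where only septal position is available, the protocol yields a category and no pressure in mmHg. These points are right, and the fix has to cover them.

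**Conclusion.** The gap is real and should be closed before unblinding. PAP comes only from echo, an echo may be cancelled because the infant is unstable, and the plan has no rule for that or for death before 72 hours. A simple comparison of available changes may be biased in either direction. At moderate correlation (0.5) and the assumed missing rates, the bias is 0.04-0.12 SD against a detectable difference of 0.68 SD. The 20% type I error needs correlation 1. All of these sizes rest on assumed inputs.

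Three stronger readings are not supported:

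- A reader might infer that the plan restricts the analysis to infants with an echo, so that the sickest and the early deaths drop out. No such restriction is written. Complete-case analysis is the natural reading of an unspecified plan, and a delayed or earlier scan may still supply a value.
- A reader might take the understatement of 13-18% as the size of the problem. It is one corner of the assumed inputs. The same formula gives overstatements of 18% to 100% elsewhere.
- A reader might take a direction from the hypotension rates under Known Safety Profile of iNO. They come from another study, and nothing links them to cancelled scans in the first 72 hours.

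**What to change.** Amend the Secondary Objective Analysis as follows:

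- Analyse PAP in all randomised infants with a repeated-measures model using every echo from gas start to 84 hours, delayed ones included, in the windows of Study Visits. Covariates are baseline PAP and the randomisation strata (gestational age and severity of pulmonary hypertension). State that the model assumes missingness is explained by observed data.
- Add a rank-based sensitivity analysis. Death before 72 hours ranks worst, and having no echo because of instability ranks next worst. Infants assessed only by septal position are placed by their protocol category, moderate or severe.
- Record the reason for each missing echo and report it by arm.
- Say whether clinically ordered echoes count after randomisation, and square the all-randomised set with the exclusion of withdrawn infants.
- Reconcile the echo schedule in Study Visits, which runs regardless of treatment length, with the endpoint section: "Arterial pressure and oxygen saturation will be measured up to 2-weeks or until the treatment is discontinued, whichever is shorter." Otherwise it is unclear whether a scan after treatment ends counts.

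The clinical rule on echo safety is left unchanged. The cost is wording in the analysis plan and one data field. The small downside is that the ranking is a convention, so it stays a sensitivity analysis. The reason for a missed scan is best recorded at the time, because it may be hard to recover later.

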## Provisions to Protect the Privacy Interest of Subjects

Subjects will be assigned a study number for collecting data. All precautions will be taken to make sure that only authorized individuals will have access subject research records. The collection of sensitive information about subjects will be limited to the minimum necessary to achieve the aims of the research and no unnecessary sensitive information will be collected.

## Early Withdrawal of Subjects

### Investigator Withdrawal of Subjects

- A. The following stopping criteria will be followed: Patient experiences a serious adverse event (defined per regulation) related to study drug
- B. Patient experiences any one of the following:
  - I. Pulmonary edema due to worsening of left ventricular dysfunction
  - II. Elevated met Hb level (>5%) on 2 samples 6 hours apart or > 7.5% on a single reading
  - III. If nitrogen di-oxide (NO2) concentration is more than 3 ppm for 6 hours or more than 5 ppm on a single reading
- C. Investigator judgement

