#### **Exclusion Criteria:**

1. Death prior to the 48 hours of age
2. Chromosomal or major congenital anomalies
3. Myocardial Dysfunction seen on screening echocardiogram
4. Infants dependent on right to left shunting of blood or any complex cardiac defect
5. Mother is COVID-19 positive

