About 1/3 of term and near-term infants with pulmonary hypertension may not respond to iNO. We will evaluate the effectiveness of iNO treatment by recording changes in serial echocardiogram and in mean airway pressure (MAP),  $\text{FiO}_2$ ,  $\text{SpO}_2/\text{FiO}_2$  ratio, and oxygenation index (OI) before and at  $24 \pm 6$ ,  $48 \pm 6$ , and  $72 \pm 12$  hours after beginning therapy. Non-responders will be defined as no improvement in pulmonary artery pressure or cardiac function on three serial echocardiograms and lack of 10% improvements from baseline for MAP,  $\text{FiO}_2$ ,  $\text{SpO}_2/\text{FiO}_2$  ratio and OI at  $72 \pm 12$  hours after starting treatment. Once an infant is identified as a non-responder, we will start weaning treatment (iNO or placebo) as described in our iNO weaning plan given below. It is important because even in "non-responders," one can still see significant rebound pulmonary hypertension with iNO discontinuation. If pulmonary hypertension is noted on subsequent echocardiograms, study intervention will not be resumed for non-responders. However, there is no restriction on clinical team to start iNO if needed based on clinical criteria.

During the course of hospitalization, all infants will receive standard of care and will be monitored as per NICU monitoring. Per AdventHealth NICU standardized guidelines, target oxygen saturations for  $\leq 32$  weeks PMA is 86-92%. We will follow these guidelines while the subject is receiving supplemental oxygen.

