## Adverse Event Reporting

An adverse event is defined as “any untoward medical occurrence associated with the use of a drug in humans, whether or not considered drug related.”

A serious adverse event is defined as an adverse event “if, in the view of the investigator, it results in any of the following outcomes: Death, a life-threatening adverse event, inpatient hospitalization or prolongation of existing hospitalization, a persistent or significant incapacity or substantial disruption of the ability to conduct normal life functions, or a congenital anomaly/birth defect. Important medical events that may not result in death, be life-threatening, or require hospitalization may be considered serious when, based upon appropriate medical judgment, they may jeopardize the patient or subject and may require medical or surgical intervention to prevent one of the outcomes listed in this definition. Examples of such medical events include allergic bronchospasm requiring intensive treatment in an emergency room or at home, blood dyscrasias or convulsions that do not result in inpatient hospitalization, or the development of drug dependency or drug abuse.”

Adverse events that meet criteria for reporting will be submitted to the FDA and/or IRB as applicable. Given this high-risk patient population, a number of adverse events are expected. The key monitoring function will be to assess whether evidence is accruing that suggests a differential adverse event rate associated with treatment. AE's collected include elevated met hemoglobin or nitrogen dioxide, rebound pulmonary hypertension after discontinuing iNO, myocardial dysfunction/heart failure, hypotension, pulmonary hemorrhage, pneumothorax, PDA (if treated), NEC (stage 2b or 3), culture proven sepsis (treated with antibiotics  $\geq$  5 days), IVH (grade III or IV), ROP (severe), death, cardiac arrest or other life-threatening events. These adverse events will be collected from the time the subject starts intervention or placebo through the end of study participation (at 36 weeks corrected gestational age) and will be documented in the subject's chart.

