#### **Severity Grading School for Adverse Events:**

Adverse event severity will be graded as below

Classification	Examples
Mild (Grade 1) infants are asymptomatic or have mild symptoms associated with study intervention that require clinical or diagnostic observations only; no intervention indicated.	
 
• Methemoglobinemia >2%
 
• NO2 > 1.5
 
• Hypokalemia <3
 
• Left Ventricular Dysfunction: Ejection Fraction decrease by 20%
 
• Thrombocytopenia: Platelets <100,000
 
• Hyperbilirubinemia in the absence of other known risk factors that requires single phototherapy
 
• Mild Hypotension (mean BP < # gestation weeks) that requires no treatment
 

Moderate (Grade 2) if infants have moderate symptoms that require discontinuing study intervention, non-urgent treatment or intervention	
 
• Methemoglobinemia >3%
 
• NO2 > 2
 
• Hypokalemia <2.7
 
• Left Ventricular Dysfunction: Ejection Fraction decrease by 30%
 
• Thrombocytopenia: Platelets <50,000
 

Current Version 9/10/2020  
Date:

IRBNet #: 1170748

Previous Version  
Date:

Page 20 of 25

	
 
Hyperbilirubinemia in the absence of other known risk factors that requires double phototherapy
 
Moderate Hypotension (mean BP < # gestation weeks) that requires IV fluid boluses after starting intervention
 

Severe (Grade 3): Infants developed severe or medically significant symptoms that is not immediately life threatening but require treatment or intervention.	
 
Methemoglobinemia >5%
 
NO2 > 3
 
Hypokalemia <2.5
 
Left Ventricular Dysfunction: Ejection Fraction decrease by 40%
 
Thrombocytopenia: Platelets <30,000
 
Hyperbilirubinemia in the absence of other known risk factors that requires triple phototherapy
 
Severe Hypotension (mean BP < # gestation weeks) that require single cardiotropic infusion after starting the study intervention
 

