Life Threatening (Grade 4): A complication that is life threatening and requires urgent intervention	
 
Methemoglobinemia >7.5%
 
NO2 > 5
 
Hypokalemia <2
 
Left Ventricular Dysfunction: Ejection Fraction decrease by 50%
 
Thrombocytopenia: Platelets <30,000+ skin or mucosal bleeding
 
Hyperbilirubinemia in the absence of other known risk factors that requires exchange transfusion
 
Severe Hypotension (mean BP < # gestation weeks) that require multiple cardiotropic infusions after starting the study intervention
 

Death (Grade 5): Any death that is directly related to study intervention	
 
Any death that cannot be explained by the existing clinical status (Sepsis/ resistant respiratory failure etc.) and directly related to iNO toxicity (all points mentioned above)
 

Relatedness/Causality of an adverse event will be determined and classified below

Classification	Definition
Related	There is an association between the event and the administration of investigational study drug, plausible mechanisms for the event to be related to the investigational study drug and causes other than the investigational study drug have been ruled out, and/or the event reappeared on re-exposure to the investigational study drug.
Possibly related	There is an association between the event and the administration of the investigational study drug and there is a plausible mechanism for the event to be related to investigational study drug, but there may also be alternative

Current Version 9/10/2020 IRBNet #: 1170748  
Date:

Previous Version Page 21 of 25  
Date:

	etiology, such as characteristics of the subject's clinical status or underlying disease.
Unlikely related	The event is unlikely to be related to the investigational study drug and likely to be related to factors other than investigational study drug.
Not related	The event is related to an etiology other than the investigational study drug (the alternative etiology will be documented in the study subject's medical record).

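### The fixed stopping list has no ejection-fraction cut-off, so a life-threatening fall without pulmonary edema is stopped only by judgement, and infants stopped under the list then leave the final analysis

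*Combined protocol and SAP*

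**What the plan says.** All places are in the combined protocol and SAP.

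- **Investigator Withdrawal of Subjects.** Criterion A is a serious adverse event related to study drug. Criterion B is a fixed list of three items. Criterion C is investigator judgement. Item B.I reads "Pulmonary edema due to worsening of left ventricular dysfunction". Items B.II (methemoglobin) and B.III (nitrogen dioxide) are numeric.
- **Severity grading table.** EF falls of 20, 30, 40 and 50% are Grades 1 to 4. The Grade 3 entry is "Left Ventricular Dysfunction: Ejection Fraction decrease by 40" percent. The Grade 4 entry, in the life-threatening class, is "Left Ventricular Dysfunction: Ejection Fraction decrease by 50" percent. The Grade 2 definition mentions discontinuing the study intervention, next to non-urgent treatment or intervention.
- **Exclusion Criteria, Step 1.** The list includes "Myocardial Dysfunction seen on screening echocardiogram".
- **Potential Risks.** "We will start weaning iNO treatment if worsening of hemodynamic status is noted on serial echocardiograms based upon the recommendations of our cardiologists".
- **Adverse Event Reporting.** An event is serious if "in the view of the investigator, it results in any of the following outcomes"; a life-threatening event is on that list.
- **Study Visits.** Non-responders, who are weaned, are defined partly by "no improvement in pulmonary artery pressure or cardiac function on three serial echocardiograms". The wean goes first to 15 ppm, then: "Weaning will continue to 10, 5, 4, 3, 2 and 1 ppm every 4 hours".
- **Data Collection and Follow-up for Withdrawn Subjects.** Withdrawn infants are left out of the final analysis. **Mitigation of Risks** applies intention to treat to infants who are unmasked.

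**The concern.** B.I is the only fixed cardiac criterion, and it acts once edema is present. It also speaks of worsening dysfunction, in infants whom screening is meant to have shown free of it. Dysfunction that first appears on treatment, seen on echocardiogram without edema, has no fixed line even at the level the protocol itself calls life threatening. Two infants with the same large EF fall could be handled differently, and the record would show no rule that was followed or broken.

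The grading table adds an unresolved signal. Its Grade 2 definition names discontinuation, and a 30% EF fall is a Grade 2 example, but the stopping list does not refer to the table.

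The analysis is also affected. The stopping criteria sit under early withdrawal, and withdrawn infants are excluded from the final analysis. Two of the three fixed items (methemoglobin and nitrogen dioxide) arise mainly from the active gas, and criterion A requires relatedness to study drug. Exclusion after randomization would therefore fall mainly on the iNO arm and can bias the comparison of death or bronchopulmonary dysplasia (BPD).

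**Working it through.** **1. Severity table against stopping list**

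| Graded item | Grade 3 | Grade 4 | Fixed stop (criterion B) |
|---|---|---|---|
| Methemoglobin | >5% | >7.5% | >5% twice, 6 h apart, or >7.5% once |
| Nitrogen dioxide | >3 | >5 | >3 ppm for 6 h, or >5 ppm once |
| LV dysfunction | EF down 40% | EF down 50% | Pulmonary edema; no EF value |
| Hypokalemia, thrombocytopenia, hyperbilirubinemia, hypotension | graded | graded | none |

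Three of the seven graded items have a line in criterion B. Two of those three carry the table's Grade 3 and 4 numbers; the LV line does not. LV dysfunction is also the only one of the seven that bars entry.

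**2. Routes to a stop before edema**

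- Weaning under Potential Risks needs no minimum EF fall, but rests on the cardiologists' recommendation.
- Criterion A: at a 50% fall the Grade 4 label largely settles seriousness. Relatedness remains a judgement, and the criterion does not say whether the class of possibly related counts.
- Criterion C is judgement by definition.
- The non-responder rule also requires less than 10% improvement in the respiratory indices at 72 ± 12 h. It detects lack of response, not cardiac harm.
- The Grade 2 wording is not an automatic stop. Grade 2 methemoglobin is >3%, below the fixed stop of >5% on two samples.

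**3. Which EF fall is meant**

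The table does not say whether the percentage is relative or absolute. At an assumed screening EF of 55 to 70%:

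- 50% relative: 0.5 × 55 = 27.5% to 0.5 × 70 = 35%.
- 50 points absolute: 55 − 50 = 5% to 70 − 50 = 20%.

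The absolute reading would make the cut-off far more extreme, so the rule should say relative.

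**4. Opportunity to see a fall**

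Scans are planned every 24 to 48 h (± 12 h) to day 14 of life. For an infant on gas throughout, starting on day 2 to 4, that is nominally (14 − 4)/2 = 5 to (14 − 2)/1 = 12 scans. Scans may be delayed or cancelled in unstable infants.

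**5. Time on gas after a decision to wean**

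From 20 ppm the levels are 15, 10, 5, 4, 3, 2 and 1: 7 × 4 h = 28 h on the standard schedule.

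**6. Effect on the primary comparison**

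The sample-size section assumes 80% in the placebo arm and a 30% relative reduction: 0.80 × 0.70 = 56%, a 24-point difference, with 34 infants per arm.

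- *Keeping a stopped iNO infant.* If that infant loses the whole assumed benefit, dilution is 24/34 = 0.71 point. One infant is 1/34 = 2.9% of the arm.
- *Excluding a stopped iNO infant.* Take 19 of 34 with the outcome (0.56 × 34 = 19.04), or 55.9%. Dropping one who has it gives 18/33 = 54.5%, 1.3 points in favor of iNO. Dropping one who does not gives 19/33 = 57.6%, 1.7 points against. The shift is systematic if stopped infants differ in prognosis.

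**7. Enrollment pause**

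Enrollment pauses when two or more infants are discontinued from the study for safety concerns. If each of 68 infants had probability p of a counted EF stop, P(at least 2) = 1 − (1 − p)^68 − 68p(1 − p)^67. For assumed p of 1%, 2% and 5% this is 15%, 40% and 86%. Automatic counting could therefore be costly.

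**The case against.** The strongest reply is that judgement is the right tool here. Methemoglobin and nitrogen dioxide are direct products of the gas, so fixed numbers suit them; an EF fall in a very preterm infant can have many causes. Potential Risks says heart failure on iNO is seen only with ischemic heart disease or myocardial dysfunction, and the adverse-event section ties the edema event to LV dysfunction that was already present. Those infants are excluded, so the remaining risk should be low. Cardiologist-led weaning can also act on a fall smaller than any listed cut-off, and a Grade 4 fall already looks serious under criterion A.

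Most of this stands, and it limits the point. A reader might infer that an infant with a falling EF would stay on study gas until edema develops. The documents do not support that: the plan commits to weaning on echocardiographic worsening, serious events go to the medical monitor, and the safety committee reviews events at 50% enrollment. Nor do the documents require a fixed stop at a 40% fall, or automatic counting of each such stop toward the enrollment pause. Those are debatable trade-offs, as the pause probabilities show. A reader might also take the Grade 2 wording as a mandatory stop at a 30% fall; the methemoglobin comparison argues against that.

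What the reply does not answer is the top of the scale. At the protocol's own life-threatening level, a fixed line takes little from the cardiologists and removes dependence on a relatedness call. Nor does it address the exclusion of stopped infants from the analysis.

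**Conclusion.** The point holds as a modest missing backstop: the response to LV dysfunction exists, but no fixed number guarantees it short of edema, and the stopping list and the Grade 2 wording are not reconciled. The number of infants affected cannot be estimated from the documents and may be small.

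The analysis rule deserves correction in its own right. It removes randomized infants for reasons that arise mainly in one arm, and it is out of step with the intention-to-treat handling of unmasked infants. This assumes that an infant stopped by the investigator counts as withdrawn, which the section headings imply. The size of any bias depends on how many are stopped and on their outcomes; the shift of 1.3 to 1.7 points per iNO infant rests on the plan's assumed 56%.

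**What to change.** 1. **Stopping list.** Reword B.I as: pulmonary edema with new or worsening LV dysfunction, or EF at least 50% (relative) below the screening value. Record EF at screening and on each serial echocardiogram while gas is on. Stop by a controlled wean, because the protocol warns of rebound pulmonary hypertension. Keep cardiologist-led weaning for smaller falls. State that the Grade 2 mention of discontinuation is not an automatic stop. Leave the enrollment-pause rule on its existing terms.
2. **Analysis set.** Amend the section on withdrawn subjects so that infants whose study gas is stopped under the investigator criteria stay in the final intention-to-treat analysis, in their randomized arm, with death or BPD ascertained at 36 weeks postmenstrual age.

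The cost is mainly wording, plus EF as a listed measurement, which the grading table already presupposes. No new scans are required. A few infants may stop gas for EF falls with other causes; each such iNO infant dilutes the assumed 24-point difference by at most about 0.7 point.
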